- Proportion of patients with disease resolution on Day 14. Disease resolution is defined as patients who are alive and have a score of 6, 7, or 8 on the NIAID 8-point ordinal scale.
- All-cause mortality rate at Day 14 and Day 60
- Change of clinical status related to COVID-19 on Day 14 compared with baseline according to the NIAID 8-point ordinal scale as listed above
- Proportion of patients requiring invasive ventilation (mechanical ventilator and/or ECMO), or who are not alive on Day 14 or Day 28
- Proportion of patients in each category of the NIAID 8-point ordinal scale
- Time to (first) improvement of at least 1 category on the NIAID 8-point ordinal scale (until Day 28). Patients who did not improve at least 1 category on the NIAID scale or die before Day 28 will be censored at Day 28.
- The odds ratio between MP1032 and SoC and placebo and SoC for the number of patients with clinical status improvement from baseline on the NIAID 8-point ordinal scale (ie, an improvement of at least 1 category) at Day 14 and Day 28
- Total duration of hospitalization on Day 28 and Day 60 (from baseline to discharge; with death censored on the last day of the observed period at Day 28 or Day 60, respectively)
- Proportion of patients alive and testing negative for COVID-19 on Day 14, Day 28, and Day 60

This document is confidential.

Page 32 of 80

- Safety and tolerability assessed by:
 - Cumulative incidence of TEAEs (summarized by seriousness, severity, relationship to the study medication, outcome, and duration)
 - Vital sign parameters
 - Clinical laboratory parameters
 - Physical examination findings
- MP1032 plasma concentrations and PK parameters (if possible) including maximum observed plasma concentration, area under the concentration-time curve, elimination parameters, apparent body clearance, apparent volume of distribution, trough concentration, average observed plasma concentration at steady state, and other relevant PK parameters assessed via MP1032 plasma exposure on Day 1 and Day 7 in a PK subset of patients

Exploratory endpoints of this study are:

- Change in saturation of oxygen (SpO₂)/fraction of inspired oxygen (FiO₂) ratio (for patients alive) on Day 14 or Day 28 compared with baseline
- Total number of days in the intensive care unit (ICU)
- Duration of invasive mechanical ventilation
- Duration of ECMO

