9.3 Measures to Minimize Bias: Randomization and Blinding

9.3.1 Randomization

The randomization of patients to treatment groups will be performed centrally by an IWRS using a randomization scheme that will be produced by an unblinded, independent statistician. During the randomization process, IWRS will assign a randomization number. Each patient will be assigned one kit number at randomization and a second kit number at the Day 14 visit. The study drug kits will contain the respective blinded treatment available at the study site. Further information on IWRS process will be provided in the IWRS Manual.

Approximately 120 patients will be randomly assigned (2:1) as follows:

- Arm A (300 mg MP1032 BID plus SoC): approximately 80 patients
- Arm B (placebo BID plus SoC): approximately 40 patients

The stratification factor for randomization will include baseline COVID-19 severity (moderate versus severe) and age-class (aged ≤ 65 years versus > 65 years). COVID-19 severity will be determined using the following criteria:

- Moderate COVID-19:
 - Positive SARS-CoV-2 testing by standard RT-PCR assay or equivalent test
 - Symptoms of moderate illness with COVID-19, which could include any symptom of mild illness or shortness of breath with exertion

This document is confidential.

Page **43** of **80**

MetrioPharm AG	MP1032-CT05
MP1032	Protocol v2.0 - France

- Clinical signs suggestive of moderate illness with COVID-19, such as respiratory rate ≥20 breaths per minute, SpO₂ >93% (on room air at sea level, if possible), heart rate ≥90 beats per minute
- No clinical signs indicative of severe or critical COVID-19
- Severe COVID-19:
 - o Positive SARS-CoV-2 testing by standard RT-PCR assay or equivalent test
 - Symptoms suggestive of severe systemic illness with COVID-19, which could include any symptom of moderate illness or shortness of breath at rest, or respiratory distress
 - Clinical signs indicative of severe systemic illness with COVID-19, such as respiratory rate ≥30 breaths per minute, heart rate ≥125 beats per minute, SpO₂ ≤93% (on room air at sea level, if possible), PaO₂/FiO₂ <300, or diagnosed with ARDS (according to the Berlin definition; see Table 3)
 - No criteria met for critical COVID-19

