5 STATISTICAL ANALYSIS

The statistical analysis plan (SAP) will provide further details regarding the definition of analysis variables and analysis methodology to address all study objectives. The SAP will be finalized before any statistical output (eg, DSMB output) is produced. The SAP will serve as a companion document to the protocol. The SAP will further describe the statistical analyses. All data will be included with the final CSR.

The statistical evaluation will be performed using SAS® software version 9.4 or higher

(CCI[®]CCI).

Summary statistics will be presented by treatment group. Continuous and ordinal variables will be summarized by the number of patients (N), mean, standard deviation, median, minimum, and maximum for actual values and change from baseline. Additionally, for ordinal data, the number and percentage of patients in each category will be presented. Binary and categorical variables will be summarized for each treatment group by presenting the number and percentage of patients in the categories.

Statistical tests for comparison between treatments will be performed using a two-sided alpha level of 10%. No adjustment for multiple testing will be applied in this descriptive proof-of-concept study.

151 Determination of Sample Size

The primary efficacy endpoint "proportion of patients with disease progression on Day 14" is assumed to be 10% in the 300 mg MP1032 BID plus SoC treatment group (Arm A) and 30% in the placebo plus SoC treatment group (Arm B). Using the Chi-square test with type I error alpha=10% two-sided for this proof-of-concept study and 2:1 randomization ratio, with 114 randomized patients (76 in Arm A and 38 in Arm B) a statistical power of 83% can be achieved. Considering about 5% early study terminations, the necessary sample size to randomize results is 120 patients in total (80 in Arm A and 40 in Arm B). If during the conduct

This document is confidential.

Page 68 of 80

MetrioPharm AG	MP1032-CT05
MP1032	Protocol v2.0 - France

of the study the early study termination rate is higher than the estimated 5%, then an increase in the randomized number of patients may be necessary.

Sample size estimation was performed using nQuery 8, Version 8.6.1.0.

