Missing data on Day 14 resulting from study termination before Day 14 are not expected. However, in case they happen, such monotone missings will be imputed by multiple imputation using information from similar patients of the same treatment group. Missing post-baseline data for patients randomized but not treated will be imputed by the respective baseline value (baseline observation carried forward [BOCF]). They comparison between the treatment groups will be performed on the ITT after imputation of missing values using MH test for common risk difference considering the 4 strata resulting from the 2 randomization stratification factors disease severity (moderate versus severe) and age-class (aged ≤ 65 years versus > 65 years). The 95% confidence intervals will be provided for the risk difference.

Similar MH analyses and presentation of 95% confidence intervals will be applied to the main estimand of the first key secondary efficacy endpoint, which is defined as a binary variable indicating disease progression (death or respiratory failure) at Day 28, and the main estimand of the second key secondary efficacy endpoint that is defined as a binary variable indicating disease resolution (alive and have a score of 6, 7 or 8 on NIAID) at Day 28. Intercurrent events that lead to study drug discontinuation and/or switch to other treatment before Day 28 will be handled

This document is confidential.

Page 70 of 80

MetrioPharm AG	MP1032-CT05	
MP1032	Final	
MetrioPharm AG	MP1032-CT05	
MP1032	Protocol v2.0 - France	

using the treatment-policy strategy for these 2 estimands (ie, the NIAID score at Day 28 will be used for definition of the failure or response, respectively) in such patients. Missing data on Day 28 will be imputed by multiple imputation using information from similar patients of the same treatment group. Missing post-baseline data for patients randomized but not treated will be imputed by BOCF.

A similar MH approach and presentation of 95% confidence intervals as described above will be applied also to the main estimand of the third key secondary efficacy endpoint, which is the all-cause mortality at Day 28. Intercurrent events that lead to study drug discontinuation and/or switch to other treatment before Day 28 will be handled using the treatment-policy strategy (ie, the life status at Day 28 will be considered). No missing data of life status on Day 28 is expected.

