This document is confidential.

Page 71 of 80

MetrioPharm AG MP1032

proportion of patients in each NIAID category, and the proportion of patients alive and testing negative for COVID-19 on Day 14, Day 28, and Day 60, respectively, will be compared between the treatment groups using MH test. Overall survival, time to (first) improvement of at least 1 category on the NIAID scale and total hospitalization duration (from baseline to discharge; with death censored on last day of the observed period – at Day 28 or Day 60, respectively – depending on the analyses) will be summarized using the Kaplan-Meier method and will be compared between treatment groups using log-rank tests. Additionally, Cox proportional hazards model will be applied with treatment and the 2 stratification factors as covariables.

The odds ratio between MP1032 and SoC and placebo and SoC for the number of patients with clinical status improvement from baseline on the NIAID 8-point ordinal scale (ie, an improvement of at least 1 category) at Day 14 and Day 28 will be analyzed using a logistic regression with consideration of the 2 stratification factors.

The time to recovery of all at baseline present COVID-19 symptoms (stuffy or runny nose, sore throat, red or irritated eyes, shortness of breath, cough, low energy or tiredness, muscle or body aches, headache, chills or shivering, feeling hot or feverish, nausea, and number of times of vomit, times of diarrhea, sense of smell, sense of taste in the last 24 hours) will be presented by Kaplan-Meier estimates and figure. The change from baseline will be presented in shift tables for each single symptom, with the number and percentage of subjects in each category at post-baseline assessment time-point compared to baseline for each treatment group.

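### Time to NIAID improvement keeps living early leavers at risk until Day 28, and the log-rank test is named without the randomization strata

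*Protocol*

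**What the plan says.** Section 6.2 lists time to first improvement of at least one NIAID category, up to Day 28, among the other secondary endpoints. Its censoring rule is: "Patients who did not improve at least 1 category on the NIAID scale or die before Day 28 will be censored at Day 28". Nothing separates patients who were followed to Day 28 from patients who left the study alive before it.

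Section 15.3 states that overall survival, time to first improvement and total hospitalization duration are summarized by Kaplan-Meier and "compared between treatment groups using log-rank tests". It names no strata there. The next sentence reads: "Additionally, Cox proportional hazards model will be applied with treatment and the 2 stratification factors as covariables".

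For hospitalization duration the only stated rule concerns deaths: "with death censored on last day of the observed period".

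On the design side, Section 9.3.1 says: "The stratification factor for randomization will include baseline COVID-19 severity (moderate versus severe) and age-class". The primary Mantel-Haenszel analysis in Section 15.3 uses a "risk difference considering the 4 strata resulting from the 2 randomization stratification factors disease severity (moderate versus severe) and age-class". Section 15.1 plans for losses: "Considering about 5% early study terminations".

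**The concern.** Kaplan-Meier estimation needs each patient to leave the risk set when observation stops. Under the Section 6.2 rule, an inpatient who withdraws consent on Day 5 without improvement stays in the risk set for 28 − 5 = 23 unobserved days. That pushes the improvement curve down, and by different amounts if the arms lose different numbers of patients.

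The rule also sits badly with the protocol's own handling of missing data. For the NIAID-based primary and key secondary binary endpoints, Section 15.3 imputes leavers from similar patients of the same arm, and treats missing as failure or non-resolution only as a sensitivity analysis. For time to improvement, missing is in effect treated as never improved, and no alternative is stated.

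The log-rank wording is a second, smaller matter. The Mantel-Haenszel, covariance, logistic and Cox analyses all name the two randomization factors. The log-rank does not. When stratification factors are prognostic and the test ignores them, its variance is too large for the balance that the design has achieved. The test then rejects less often than its nominal level and loses power.

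**Working it through.** **The plan's own figure first.** The only stated power is for the Day 14 endpoint: 10% against 30%, 76 against 38 patients, two-sided 10%.
- Pooled proportion: (7.6 + 11.4)/114 = 0.1667
- Null SE: √[0.1667 × 0.8333 × (1/76 + 1/38)] = 0.0740
- Alternative SE: √[0.09/76 + 0.21/38] = 0.0819
- z = (0.20 − 1.645 × 0.0740)/0.0819 = 0.955, so power is 0.830, against the stated 83%
- Sample size: 114/0.95 = 120

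Both reproduce. The protocol gives no figure for the log-rank comparisons, so everything below rests on stated assumptions.

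**Bias of the improvement curve.** Let the improvement hazard be h, let a fraction d leave at time u, and let leaving be unrelated to improvement. The rule loses the improvements that leavers would have had between u and Day 28:

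bias = d × (mean of e^(−hu) − e^(−28h))

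Take d = 0.05 (Section 15.1) and h = 0.10 per day (assumed), so that e^(−2.8) = 0.061 and true Day 28 improvement is 93.9%.
- Leaving uniform over 28 days: mean = (1 − e^(−2.8))/2.8 = 0.335. Bias = 0.05 × (0.335 − 0.061) = 1.4 points.
- Leaving uniform over Days 1 to 14: mean = (e^(−0.1) − e^(−1.4))/1.3 = 0.506. Bias = 0.05 × (0.506 − 0.061) = 2.2 points, so the curve reads 91.7%.

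Other hazards change little. With leaving spread over Days 1 to 27, h = 0.05 gives 1.44 points and h = 0.09 gives 1.39. The bias is proportional to d. If one arm lost 10% and the other 5%, the rule alone would create a difference between arms of about 1.4 to 2.2 points.

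**Log-rank simulation.** The setup was 120 patients, 2:1 permuted blocks of 3 within 4 strata (30/20/30/20%), a base hazard of 0.09 per day and times rounded up to days. In both arms 5% left, uniformly over Days 1 to 27. There were 4000 trials per cell, tested at two-sided 10%. Stratum effects, hazard, treatment hazard ratio (1.6), block size and timing of leaving are assumptions. The Section 6.2 rule was applied in this table.

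| Stratum HR (severity/age) | Level, no strata | Level, stratified | Power, no strata | Power, stratified |
|---|---|---|---|---|
| 1 / 1 | 0.098 | 0.098 | 0.707 | 0.692 |
| 0.7 / 0.8 | 0.096 | 0.102 | 0.682 | 0.689 |
| 0.5 / 0.7 | 0.080 | 0.101 | 0.623 | 0.670 |
| 0.35 / 0.6 | 0.070 | 0.103 | 0.517 | 0.623 |

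The largest power loss is 62.3 − 51.7 = 10.6 points. The Monte Carlo standard error of a level near 0.10 is √(0.09/4000) = 0.005.

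**Does the censoring rule affect the test?** When leavers were censored at departure instead and strata were ignored, the null levels were 0.098, 0.096, 0.081 and 0.070, the same as above to within 0.001. Power was 0.737, 0.701, 0.642 and 0.528, a gain of 1 to 3 points. The rule therefore costs a little power and leaves type I error alone, given equal loss in the arms.

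**The case against.** Several points on the other side stand.

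- A reader might infer that the protocol prescribes an unstratified log-rank that fails to run at 10%. It does not say so. The strata are simply not mentioned, and the analysis plan may add them. The loss also depends on prognostic effects that the protocol does not quantify, and with none it vanishes.
- A comparison adjusted for both factors is already planned for the same endpoints through the Cox model, so that part needs no repair.
- A reader might infer that the Day 28 rule makes the tests conservative. The simulation shows no such effect on the level.
- A reader might extend the rule to every time-to-event endpoint. It governs time to improvement only. For hospitalization duration just deaths are moved to the last day, and nothing is said of living leavers.
- Few patients are affected. Everyone is hospitalized at entry, so baseline NIAID is at most 6, and discharge alive scores 7 or 8. A patient lost after discharge has already had the event. Patients who stop study drug are expected to stay in follow-up, and Section 15.3 does not expect missing Day 14 data from early termination.
- Carrying deaths to Day 28 is a sound way to keep them as never improved.

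What remains is that the Section 6.2 rule is written out rather than left open, and its literal reading covers the inpatient who withdraws unimproved.

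**Conclusion.** The concern holds in a limited form. The censoring rule biases the Kaplan-Meier improvement proportion down by about 1.4 to 2.2 points at the planned 5% terminations. This assumes a hazard of 0.10 per day and leaving unrelated to improvement. The bias is smaller if most leavers have already been discharged. It is larger if leavers are mainly unimproved inpatients, though it cannot exceed the 5% who leave. Type I error is unchanged when the arms lose equally.

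If severity and age-class are prognostic, a log-rank run without strata would have an actual level of about 7.0% to 9.6% and lose up to about 11 points of power. With no prognostic effect it loses nothing. Naming the strata is a clarification that costs nothing and matches the other analyses.

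These are secondary endpoints in a study that the protocol calls descriptive. Nothing here touches the primary analysis or the sample size.

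**What to change.** In Section 6.2 (and the matching synopsis entry), replace the rule for time to improvement with: *Deaths without prior improvement are censored at Day 28; patients who leave the study alive without improvement are censored at their last NIAID assessment.*

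In Section 15.3, describe the log-rank tests as stratified by the two randomization factors, severity and age-class. Leave the Cox model as it is. Carry both statements into the analysis plan.

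The cost is two sentences. No new data, visits or patients are needed.

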5.4 Safety Analysis

All safety parameters will be summarized descriptively by treatment group for the entire study period.

Study drug duration and SoC therapies will be described for each treatment group.

All reported AEs will be coded into preferred term (PT) and grouped by SOC using the most recent Medical Dictionary for Regulatory Activities version. An overall summary will be provided with the number and percentage of patients reporting TEAEs, serious TEAEs, treatment-related TEAEs, TEAEs leading to withdrawal, and TEAEs leading to death. For patients with any serious TEAE and for patients with any related serious TEAE exposureadjusted events rates will be calculated and compared between treatment groups using the risk ratio [(300 mg MP1032 BID plus SoC) / (placebo plus SoC)] with respective 95% confidence intervals. This comparison will also be performed for the rate of rehospitalization which is considered a serious AE. The number and percentage of patients with TEAEs, serious TEAEs, TEAEs leading to withdrawal, and treatment-related TEAEs will be summarized by SOC and PT for each treatment group, and total. In these tables, the incidence of TEAEs by SOC and PT will also be included. TEAEs will also be summarized by maximum severity and relationship to study drug. Events with missing onset dates will be considered as TEAEs. If a patient experienced >1 occurrence of the same AE, the occurrence with the greatest severity and the closest association with the study drug will be used in the corresponding summary tables. In case that for one AE several AE episodes with changing severity is reported, an aggregation of all respective episodes to one AE will be performed before summarization. The worst severity and the worst causality will be assigned to the aggregated AE and used for the respective AE summaries. All reported AE episodes will be listed by patient, along with information regarding onset, duration, severity and relationship to study drug, action taken with study drug, treatment of event, and outcome. Additionally, the aggregated AEs with the resulting worst severity and worst relationship will be included in the AE listings.

Vital signs including SpO₂ (%) will be summarized using descriptive statistics, including mean values and mean change from baseline values. Clinical laboratory data of local laboratories will be presented with the number and percentage of patients with values below, within, or above the normal range at each time point. Additionally, a shift table of the number and percentage of patients with normal and abnormal, and clinically significant abnormal values at each scheduled postbaseline visit compared with the normal/abnormal/clinically significant abnormal categorization at baseline will be provided by treatment group. Summarizing of clinical laboratory data of local laboratories using descriptive statistics, including mean values and mean change from baseline values will be only possible after normalization of the values using a reference laboratory. Details for normalization will be provided in the SAP.

Summary tables will be provided for concomitant medications.

This document is confidential.

Page 73 of 80

MetrioPharm AG MP1032

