5.2.2 Clinical Studies

MP1032 so far has been investigated in 3 clinical studies, including a first-in-human study (MP1032-CT01; EudraCT-No.: 2014-004606-15) with a single ascending dose and a multiple ascending dose part, as well as 2 studies in patients with moderate-to-severe psoriasis: a 6-week, Phase IIa, pilot study (MP1032-CT02; EudraCT-No.: 2015-005159-28) and a 3-month, Phase II study (MP1032-CT04; EudraCT-No.: 2017-003484-36).

This document is confidential.

Page 27 of 80

Among the subjects enrolled in MP1032 studies, 146 subjects were administered MP1032 orally. Among them, 24 male subjects participated as healthy volunteers in the Phase I study, while both male (n=89) and female (n=33) patients with psoriasis participated in the Phase II studies. The age of participants administered MP1032 ranged from 18 to 68 years. Pregnant and breastfeeding women, as well as children and adolescents have not been included in the studies.

The highest single dose of MP1032 administered was 600 mg, applied to healthy volunteers. The highest repeated dose was 300 mg MP1032 BID, applied to both healthy volunteers (7 days) and patients with psoriasis (3 months).

No serious adverse events (SAEs) occurred in any of the subjects administered MP1032.

No deaths occurred in the scope of the MP1032 clinical development program.

MP1032 was well tolerated in all studies, and safety analyses did not reveal any clinically important safety issues. In general, incidence, intensity, causality, and spreading of TEAEs over system organ classes (SOCs) were comparable between groups. In the recent Phase II study, the incidence, intensity, relationship to investigational medicinal product (IMP), and causality to IMP for adverse events (AEs) were even lower for both MP1032 dose groups compared with those of the placebo group and statistically significantly lower for the 300 mg MP1032 group compared with the placebo group.

None of the potential risks arising from preclinical data could be confirmed with clinical data.

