15.8 Data Monitoring Committee

An independent DMC will be established by the sponsor or designee to review accumulating study data at regular intervals (as per the DMC charter) throughout the study to ensure the safety of patients and review overall study conduct. Additional data may be reviewed that are related to efficacy, but the DMC will only be reviewing data for risk-benefit purposes. Members will include experts in drug safety and/or medical specialist and biostatistics, who are not participating in this study and do not have affiliation with the investigators or the sponsor. The DMC can recommend in writing to the sponsor whether to continue, modify, or stop the clinical study on the basis of safety considerations. The pre-specified study stopping rules for the trial are defined as follows:

- death (not including disease progression) in any patient in whom the cause of death is judged to be related to the study drug by investigator
- the occurrence in any patient of a SAE whose causal relationship (ie, without a plausible alternative explanation) to the study drug is judged to be related by investigator
- two occurrences of a clinically significant Grade 3 or higher laboratory abnormality assessed to be related to the study drug by investigator.

This document is confidential.

Page 74 of 80

MetrioPharm AG	MP1032-CT05
MP1032	Protocol v2.0 - France

The DMC's specific duties will be fully described in a DMC charter.

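### Related serious TEAEs are compared between arms only by a rate ratio, which at low event rates will often be 0, infinite or 0/0 with 80 against 40 patients

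*Protocol*

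**What the plan says.** Section 15.4 (Safety Analysis) reads the same in the French and Bulgarian versions of the protocol. It takes patients with any serious TEAE and, separately, those with a related one: "for patients with any related serious TEAE exposureadjusted events rates will be calculated and compared between treatment groups using the risk ratio". The ratio is MP1032 plus SoC over placebo plus SoC, "with respective 95% confidence intervals". The same comparison is applied to rehospitalization.

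For related serious TEAEs the section names no other between-arm measure. It gives no interval method and no rule for an arm without events. Outside this comparison it plans summaries of TEAEs by relationship to study drug and patient-level listings of every AE episode.

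Section 9.3.1 sets the arm sizes: "Arm A (300 mg MP1032 BID plus SoC): approximately 80 patients" and "Arm B (placebo BID plus SoC): approximately 40 patients".

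**The concern.** A ratio needs at least one event in the denominator to have a finite value, and at least one in each arm to be finite and non-zero. Related serious events may be few in a trial of 120 patients, and the 2:1 allocation puts the smaller arm in the denominator. The awkward outcome is also the one of most interest, with some events on MP1032 and none on placebo: the planned estimate is then infinite. If neither arm has an event, the estimate is 0/0 and no interval for the ratio can be formed. The one comparison chosen for drug-related serious harm could then say little or nothing, although a difference would still have a value and an interval.

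**Working it through.** **The plan's own figure.** The protocol states no calculation for related serious TEAEs. Its only stated calculation, the power in section 15.1, reproduces. With 38 and 76 patients, 30% against 10%, two-sided alpha 10%:
- pooled proportion = (38 × 0.30 + 76 × 0.10)/114 = 0.1667
- standard error under the null = √[0.1667 × 0.8333 × (1/38 + 1/76)] = 0.0740
- standard error under the alternative = √(0.21/38 + 0.09/76) = 0.0819
- power = Φ[(0.20 − 1.645 × 0.0740)/0.0819] = 0.83

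This agrees with the stated 83% and is not affected by the present point.

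**Inputs.** Arm sizes of 80 and 40 come from section 9.3.1. The per-patient rate of related serious TEAEs is not given for this population. It is an assumption here, shown from 0.5% to 5% and taken as equal in both arms. Exposure adjustment does not change whether the ratio is 0, infinite or 0/0, because that depends only on which arms have events.

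**Formulae.** With a common rate p:
- no event on placebo: b = (1 − p)^40
- no event on MP1032: a = (1 − p)^80
- ratio 0/0: a × b
- ratio 0, infinite or 0/0: 1 − (1 − a)(1 − b)

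| p | b | a | 0/0 | 0, infinite or 0/0 |
|---|---|---|---|---|
| 0.5% | 0.818 | 0.670 | 0.548 | 0.940 |
| 1% | 0.669 | 0.448 | 0.299 | 0.817 |
| 2% | 0.446 | 0.199 | 0.089 | 0.556 |
| 3% | 0.296 | 0.087 | 0.026 | 0.357 |
| 5% | 0.129 | 0.017 | 0.002 | 0.143 |

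The last column passes 50% at a common rate of about 2.25%. Column b passes 50% at 1 − 0.5^(1/40) = 1.7%.

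**If MP1032 doubles a placebo risk of 1%.** The chance of at least one event on MP1032 and none on placebo is (1 − 0.98^80) × 0.99^40 = 0.801 × 0.669 = 54%.

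**What each measure gives in sparse cases.** The difference in proportions has a Newcombe (score-based) 95% interval. The ratio has an exact conditional 95% interval, assuming 2:1 exposure.

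| Events, MP1032 vs placebo | Difference (95% CI) | Ratio (95% CI) |
|---|---|---|
| 0 vs 0 | 0.0% (−8.8% to +4.6%) | 0/0 (none) |
| 1 vs 0 | +1.25% (−7.6% to +6.8%) | infinite (0.013 to infinity) |
| 0 vs 1 | −2.5% (−12.9% to +2.5%) | 0 (0 to 19.5) |

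The two finite ratio bounds follow from (0.025/0.975)/2 = 0.013 and (0.975/0.025)/2 = 19.5.

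**The case against.** **This is a matter for the SAP.** In part, yes. The interval method and the handling of empty arms are commonly left to the SAP, and their absence from the protocol is no fault. But the choice of the ratio as the only comparison is made in the protocol, and no interval method rescues 0/0.

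**A ratio of 0 or infinity is not useless.** This stands. It is tempting to say that the interval would not exist. That is true of a log-scale Wald interval, which the protocol does not specify. An exact conditional interval gives a one-sided bound unless both arms are empty.

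**The consequence is small.** This also stands. The per-arm rates are calculated in any case and show events on one arm and none on the other. The listings hold every episode, no decision rule uses the ratio, and the protocol describes the study as descriptive. With so few events the difference is imprecise too.

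**Three stronger readings go further than the documents allow.**
- A reader might infer from section 5.2.2 that the rate must be low: "146 subjects were administered MP1032 orally" and "No serious adverse events (SAEs) occurred in any of the subjects administered MP1032". The exact one-sided 95% upper limit for 0 of 146 is 1 − 0.05^(1/146) = 2.03%. Those subjects were 24 healthy volunteers and 122 patients with psoriasis, all given MP1032. They cannot bound how often serious events in hospitalized COVID-19 patients, including those on placebo, will be rated related. Table 7 lets an event count as possibly related when the link seems improbable but cannot be excluded, so rates above 2% are plausible.
- A reader might infer from section 15.8 that the count can hardly exceed one, since a stopping rule is met by "the occurrence in any patient of a SAE whose causal relationship (ie, without a plausible alternative explanation) to the study drug". The parenthesis restricts the rule to events with no other explanation, and the DMC only recommends. Events rated possibly related can accumulate without meeting the rule.
- A reader might conclude that the comparison will most likely return no number. That requires no placebo event, which at 2% has a probability of 45%.

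**Conclusion.** The point holds as a minor one. Section 15.4 fixes a weak sole comparison for related serious TEAEs. How often it fails depends on a rate that the protocol does not give. At an equal 0.5%, 1% or 2% per arm, the ratio is 0, infinite or 0/0 in 94%, 82% or 56% of trials. At 3% or 5% it is so in only 36% or 14%. These figures assume 80 and 40 patients, equal risk and independent patients. Neither the earlier MP1032 studies nor the stopping rule settles where in that range the trial will lie.

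The loss is limited to the between-arm summary. The point does not extend to all serious TEAEs or to rehospitalization, which may be frequent enough in this population for a ratio to work.

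**What to change.** In section 15.4, for related serious TEAEs:
- Make the between-arm difference the main comparison, in proportions or in exposure-adjusted rates, with a score (for example Miettinen-Nurminen) or exact 95% interval.
- Keep the ratio, with an exact conditional 95% interval, when at least one arm has an event.
- When neither arm has an event, report each arm's exact upper limit. With the upper end of a two-sided 95% interval these would be 1 − 0.025^(1/80) = 4.5% on MP1032 and 1 − 0.025^(1/40) = 8.8% on placebo.

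The comparisons for all serious TEAEs and for rehospitalization can stay as they are. The cost is a sentence or two of wording, carried into the SAP, and one extra line of safety output from standard software. It needs no new data and does not change the sample size or trial conduct.
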